12.3. Appendix 3: Liver Safety – Study Treatment Restart or Rechallenge Guidelines

If subject meets liver chemistry stopping criteria do not restart/rechallenge subject with study treatment unless:

- GSK Medical Governance approval **is granted** (as described below),
- Ethics and/or IRB approval is obtained, if required, and
- Separate consent for treatment restart/rechallenge is signed by the subject

If GSK Medical Governance approval to restart/rechallenge subject with study treatment **is not granted**, then subject must permanently discontinue study treatment and may continue in the study for protocol-specified follow up assessments

1. Rechallenge Following Liver Stopping Events that are Possibly Related to Study Treatment

Following drug-induced liver injury, **drug rechallenge is associated with a 13% mortality across all drugs in prospective studies.** [Andrade](#), 2009 Clinical outcomes vary by drug, with nearly 50% fatality with halothane readministered within one month of initial injury. However, some drugs seldom result in recurrent liver injury or fatality.

Risk factors for a fatal drug rechallenge outcome include:

- hypersensitivity¹ with initial liver injury (e.g. fever, rash, eosinophilia)
- jaundice or bilirubin >2xULN with initial liver injury (direct bilirubin >35% of total)
- subject currently exhibits severe liver injury defined by: ALT \geq 3xULN, bilirubin \geq 2xULN (direct bilirubin >35% of total), or INR \geq 1.5
- serious adverse event or fatality has earlier been observed with drug rechallenges [Papay](#), 2009, [Hunt](#), 2010
- evidence of drug-related preclinical liability (e.g. reactive metabolites; mitochondrial impairment³)

Rechallenge refers to resuming study treatment following drug induced liver injury (DILI). Because of the risks associated with rechallenge after DILI this should only be considered for a subject for whom there is compelling evidence of benefit from a critical or life-saving medicine, there is no alternative approved medicine available, and a benefit:risk assessment of rechallenge is considered to be favourable.

Approval by GSK for rechallenge with study treatment can be considered where:

- Investigator requests consideration of rechallenge with study treatment for a subject who is receiving compelling benefit with study treatment that exceeds risk, and no effective alternative therapy is available.
- Ethics Committee or Institutional Review Board approval for rechallenge with study treatment must be obtained, as required.

- If the rechallenge is approved by GSK Medical Governance in writing, the subject must be provided with a clear description of the possible benefits and risks of study treatment administration, including the possibility of recurrent, more severe liver injury or death.
- The subject must also provide signed informed consent specifically for the rechallenge with study treatment. Documentation of informed consent must be recorded in the study chart.
- Study treatment must be administered at the dose specified by GSK.
- Subjects approved by GSK Medical Governance for rechallenge with study treatment must return to the clinic twice a week for liver chemistry tests until stable liver chemistries have been demonstrated and then standard laboratory monitoring may resume as per protocol.
- If after study treatment rechallenge, subject meets protocol-defined liver chemistry stopping criteria, study treatment should be permanently discontinued.
- GSK Medical Monitor, and the Ethics Committee or Institutional Review Board as required, must be informed of the subject's outcome following study treatment rechallenge.
- GSK to be notified of any adverse events, as per [Appendix 5](#).

2. *Restart Following Transient Resolving Liver Stopping Events NOT Related to Study Treatment*

Restart refers to resuming study treatment following liver stopping events in which there is a clear underlying cause (other than DILI) of the liver event (e.g. biliary obstruction, pancreatic events, hypotension, acute viral hepatitis). Furthermore, there should be no evidence of alcoholic hepatitis or hypersensitivity, and the study treatment should not be associated with HLA markers of liver injury.

Approval by GSK for study treatment restart can be considered where:

- Investigator requests consideration for study treatment restart if liver chemistries have a clear underlying cause (e.g., biliary obstruction, hypotension and liver chemistries have improved to normal or are within 1.5 x baseline and ALT <3xULN).
- Restart risk factors (e.g. fever, rash, eosinophilia, or hypersensitivity, alcoholic hepatitis, possible study treatment-induced liver injury or study treatment has an HLA genetic marker associated with liver injury (e.g. lapatinib, abacavir, amoxicillin/clavulanate) are reviewed and excluded
- Ethics Committee or Institutional Review Board approval of study treatment restart must be obtained, as required.
- If restart of study treatment is approved by GSK Medical Governance in writing, the subject must be provided with a clear description of the possible benefits and risks of study treatment administration, including the possibility of recurrent, more severe liver injury or death.

- The subject must also provide signed informed consent specifically for the study treatment restart. Documentation of informed consent must be recorded in the study chart.
- Study treatment must be administered at the dose specified by GSK.
- Subjects approved by GSK Medical Governance for restarting study treatment must return to the clinic once a week for liver chemistry tests until stable liver chemistries have been demonstrated and then laboratory monitoring may resume as per protocol.
- If after study treatment re-start, subject meets protocol-defined liver chemistry stopping criteria, follow usual stopping criteria instructions.
- GSK Medical Monitor, and the Ethics Committee or Institutional Review Board as required, must be informed of the subject's outcome following study treatment restart.
- GSK to be notified of any adverse events, as per [Appendix 5](#).

References:

2. Hunt, CM. Mitochondrial and immunoallergic injury increase risk of positive drug rechallenge after drug-induced liver injury: A systematic review. *Hepatology.* 2010;52:2216-2222.

12.4. Appendix 4: Genetic Research

USE/ANALYSIS OF DNA

- Genetic variation may impact a participant's response to therapy, susceptibility, severity and progression of disease. Variable response to therapy may be due to genetic determinants that impact drug absorption, distribution, metabolism, and excretion; mechanism of action of the drug; disease etiology; and/or molecular subtype of the disease being treated. Therefore, where local regulations and IRB/IEC allow, a saliva sample will be collected for DNA analysis
- DNA samples will be used for research related to GSK2879552 or GSK2879552 in combination with azacitidine or any concomitant medicines, or MDS and related diseases. They may also be used to develop tests/assays including (diagnostic tests) related to GSK2879552 or GSK2879552 in combination with azacitidine or study treatments of this drug class, and MDS. Genetic research may consist of the analysis of one or more candidate genes or the analysis of genetic markers throughout the genome or analysis of the entire genome (as appropriate)
- DNA samples will be analyzed if it is hypothesized that this may help further understand the clinical data.
- DNA samples will be analyzed for describe planned analyses. Additional analyses may be conducted if it is hypothesized that this may help further understand the clinical data.
- The samples may be analyzed as part of a multi-study assessment of genetic factors involved in the response to GSK2879552 or GSK2879552 in combination with azacitidine or study treatments of this class. The results of genetic analyses may be reported in the clinical study report or in a separate study summary.
- The sponsor will store the DNA samples in a secure storage space with adequate measures to protect confidentiality.
- The samples will be retained while research on GSK2879552 or GSK2879552 in combination with azacitidine or study treatments of this class or MDS continues but no longer than 15 years or other period as per local requirements.

12.5. Appendix 5: Definition of and Procedures for Recording, Evaluating, Follow-Up and Reporting of Adverse Events

12.5.1. Definition of Adverse Events

Adverse Event Definition:

- An AE is any untoward medical occurrence in a patient or clinical investigation subject, temporally associated with the use of a medicinal product, whether or not considered related to the medicinal product.
- NOTE: An AE can therefore be any unfavorable and unintended sign (including an abnormal laboratory finding), symptom, or disease (new or exacerbated) temporally associated with the use of a medicinal product.

Events meeting AE definition include:

- Any abnormal laboratory test results (hematology, clinical chemistry, or urinalysis) or other safety assessments (e.g., ECGs, radiological scans, vital signs measurements), including those that worsen from baseline, and felt to be clinically significant in the medical and scientific judgement of the investigator.
- Exacerbation of a chronic or intermittent pre-existing condition including either an increase in frequency and/or intensity of the condition.
- New conditions detected or diagnosed after study treatment administration even though it may have been present prior to the start of the study.
- Signs, symptoms, or the clinical sequelae of a suspected interaction.
- Signs, symptoms, or the clinical sequelae of a suspected overdose of either study treatment or a concomitant medication (overdose per se will not be reported as an AE/SAE unless this is an intentional overdose taken with possible suicidal/self-harming intent. This should be reported regardless of sequelae).
- "Lack of efficacy" or "failure of expected pharmacological action" per se will not be reported as an AE or SAE. However, the signs and symptoms and/or clinical sequelae resulting from lack of efficacy will be reported if they fulfil the definition of an AE or SAE.
-

Events NOT meeting definition of an AE include:

- Any clinically significant abnormal laboratory findings or other abnormal safety assessments which are associated with the underlying disease, unless judged by the investigator to be more severe than expected for the subject's condition.
- The disease/disorder being studied or expected progression, signs, or symptoms of

the disease/disorder being studied, unless more severe than expected for the subject's condition.

- Medical or surgical procedure (e.g., endoscopy, appendectomy): the condition that leads to the procedure is an AE.
- Situations where an untoward medical occurrence did not occur (social and/or convenience admission to a hospital).
- Anticipated day-to-day fluctuations of pre-existing disease(s) or condition(s) present or detected at the start of the study that do not worsen.

12.5.2. Definition of Serious Adverse Events

If an event is not an AE per definition above, then it cannot be an SAE even if serious conditions are met (e.g., hospitalization for signs/symptoms of the disease under study, death due to progression of disease, etc).

Serious Adverse Event (SAE) is defined as any untoward medical occurrence that, at any dose:

a. Results in death

b. Is life-threatening

NOTE:

The term 'life-threatening' in the definition of 'serious' refers to an event in which the subject was at risk of death at the time of the event. It does not refer to an event, which hypothetically might have caused death, if it were more severe.

c. Requires hospitalization or prolongation of existing hospitalization

NOTE:

- In general, hospitalization signifies that the subject has been detained (usually involving at least an overnight stay) at the hospital or emergency ward for observation and/or treatment that would not have been appropriate in the physician's office or out-patient setting. Complications that occur during hospitalization are AEs. If a complication prolongs hospitalization or fulfills any other serious criteria, the event is serious. When in doubt as to whether "hospitalization" occurred or was necessary, the AE should be considered serious.
- Hospitalization for elective treatment of a pre-existing condition that did not worsen from baseline is not considered an AE.

d. Results in disability/incapacity

NOTE:

- The term disability means a substantial disruption of a person's ability to conduct normal life functions.

| |
|--|
| 
 This definition is not intended to include experiences of relatively minor medical significance such as uncomplicated headache, nausea, vomiting, diarrhea, influenza, and accidental trauma (e.g. sprained ankle) which may interfere or prevent everyday life functions but do not constitute a substantial disruption |
| 
e. Is a congenital anomaly/birth defect
 |
| 
f. Other situations:
 
 Medical or scientific judgment should be exercised in deciding whether reporting is appropriate in other situations, such as important medical events that may not be immediately life-threatening or result in death or hospitalization but may jeopardize the subject or may require medical or surgical intervention to prevent one of the other outcomes listed in the above definition. These should also be considered serious. Examples of such events are invasive or malignant cancers, intensive treatment in an emergency room or at home for allergic bronchospasm, blood dyscrasias or convulsions that do not result in hospitalization, or development of drug dependency or drug abuse |
| 
g. Is associated with liver injury and impaired liver function defined as:
 
 ALT \geq 3xULN and total bilirubin* \geq 2xULN (>35% direct), or ALT \geq 3xULN and INR** > 1.5. 
* Serum bilirubin fractionation should be performed if testing is available; if unavailable, measure urinary bilirubin via dipstick. If fractionation is unavailable and ALT \geq 3xULN and total bilirubin \geq 2xULN, then the event is still to be reported as an SAE.
 
** INR testing not required per protocol and the threshold value does not apply to subjects receiving anticoagulants. If INR measurement is obtained, the value is to be recorded on the SAE form.
 |

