4.3.3. Dose Limiting Toxicities

An event will be considered a DLT if it occurs within the first 28 days of treatment, and meets one of the following criteria unless it can be clearly established that the event is unrelated to treatment. Subjects unable to receive at least 75% of scheduled doses (of both agents, at the intended strength) for reasons other than toxicity (e.g., acute illness, disease progression) will not be evaluable for DLT purposes:

- Grade 4 thrombocytopenia associated with clinically significant bleeding
- Any Grade 3 or greater non-hematologic toxicity
- Fatigue, asthenia, nausea, vomiting or new electrolyte disturbance that respond to standard medical care within 72 hours are exceptions
- Any toxicity considered drug related that in the judgment of the investigator and GSK Medical Monitor is dose-limiting
- Drug related toxicities that prevent subjects from taking $\geq 75\%$ of the intended doses during the first 28 days of treatment
- Treatment delay of 14 days or greater due to unresolved drug-related toxicity

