7.3.1.5. Disease-Related Events and/or Disease-Related Outcomes Not Qualifying as SAEs

An event which is part of the natural course of the disease under study (i.e., disease progression or hospitalization due to disease progression) does not need to be reported as a serious adverse event (SAE). Death due to disease under study is to be recorded on the Death electronic case report form (eCRF). However, if the underlying disease (i.e., progression) is greater than that which would normally be expected for the subject, or if the investigator considers that there was a causal relationship between treatment with study treatment(s) or protocol design or procedures and the disease progression, then this must be reported as a SAE.

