12.5.5. Evaluating AEs and SAEs

Assessment of Intensity

The investigator will make an assessment of intensity for each AE and SAE reported during the study and will assign it to one of the following categories:

- Mild: An event that is easily tolerated by the subject, causing minimal discomfort and not interfering with everyday activities.
- Moderate: An event that is sufficiently discomforting to interfere with normal everyday activities
- Severe: An event that prevents normal everyday activities. - an AE that is assessed as severe will not be confused with an SAE. Severity is a category utilized for rating the intensity of an event; and both AEs and SAEs can be assessed as severe.
- An event is defined as 'serious' when it meets at least one of the pre-defined outcomes as described in the definition of an SAE.

Assessment of Causality

- The investigator is obligated to assess the relationship between study treatment and the occurrence of each AE/SAE.
- A "reasonable possibility" is meant to convey that there are facts/evidence or arguments to suggest a causal relationship, rather than a relationship cannot be ruled out.
- The investigator will use clinical judgment to determine the relationship.
- Alternative causes, such as natural history of the underlying diseases, concomitant therapy, other risk factors, and the temporal relationship of the event to the study treatment will be considered and investigated.
- The investigator will also consult the Investigator Brochure (IB) and/or Product Information, for marketed products, in the determination of his/her assessment.
- For each AE/SAE the investigator **must** document in the medical notes that he/she has reviewed the AE/SAE and has provided an assessment of causality.
- There may be situations when an SAE has occurred and the investigator has minimal information to include in the initial report to GSK. However, **it is very important that the investigator always make an assessment of causality for every event prior to the initial transmission of the SAE data to GSK.**
- The investigator may change his/her opinion of causality in light of follow-up information, amending the SAE data collection tool accordingly.
- The causality assessment is one of the criteria used when determining regulatory reporting requirements.

Follow-up of AEs and SAEs

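### Treatment-caused worsening of expected severity must be reported as an SAE under Section 7.3.1.5 but cannot be one under Appendix 5, so AE and SAE counts may be too low

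*Protocol*

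**What the plan says.** Section 7.3.1 sends the reader to Appendix 5 for the definitions of AE and SAE.

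- **Section 12.5.1, inclusions.** The events that count as AEs begin with "Any abnormal laboratory test results (hematology, clinical chemistry, or urinalysis) or other safety assessments". Results that worsen from baseline are named, provided the investigator finds them clinically significant. Exacerbation of a pre-existing condition is also listed. An AE counts whether or not it is thought related to the product.
- **Section 12.5.1, exclusions.** Clinically significant laboratory findings are not AEs if they are "associated with the underlying disease, unless judged by the investigator to be more severe than expected for the subject's condition". The disease itself and its expected progression, signs or symptoms are excluded with the same severity exception. Neither exclusion has an exception for a causal link to treatment.
- **Section 12.5.2, first sentence.** "If an event is not an AE per definition above, then it cannot be an SAE even if serious conditions are met". The examples given are hospitalisation for signs or symptoms of the disease and death from its progression.
- **Section 7.3.1.5.** Events in the natural course of the disease are exempt from SAE reporting by default. Reporting becomes mandatory in two cases: the progression exceeds what would normally be expected, or "if the investigator considers that there was a causal relationship between treatment with study treatment(s) or protocol design or procedures and the disease progression".

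AEs and SAEs are part of the Part 1 primary endpoint (Section 3.1) and of the Part 2 safety endpoint (Section 3.2).

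**The concern.** Section 7.3.1.5 and Appendix 5 govern the same events, and the protocol does not say which takes precedence. Section 7.3.1.5 has two routes to mandatory reporting; Appendix 5 has only one of them.

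In many indications a gap about treatment-caused progression would rarely be reached. In this trial it can be. MDS is characterised by cytopenia (Section 2.1.2), Section 4.11.1 names thrombocytopenia as the primary toxicity of GSK2879552 and says azacitidine causes anaemia, neutropenia and thrombocytopenia, and progression is itself partly defined by blood counts. An investigator who believes that treatment contributed to a worsening of ordinary severity gets opposite instructions from the two texts. Following Appendix 5 leaves the event out of both the AE and the SAE counts. Sites may also resolve the conflict differently, in an open-label study.

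**Working it through.** No stated figure is in dispute, so the check sets the passages side by side.

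**Step 1. Status of a disease-associated worsening that meets a seriousness criterion.** Classify it by severity and by the investigator's view of cause.

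| Severity | Considered caused by treatment or procedures? | Section 7.3.1.5 | Sections 12.5.1 and 12.5.2 |
|---|---|---|---|
| More than expected | No | SAE report mandatory | AE, therefore SAE |
| More than expected | Yes | SAE report mandatory | AE, therefore SAE |
| As expected | No | Exempt | Not an AE, cannot be an SAE |
| As expected | Yes | SAE report mandatory | Not an AE, cannot be an SAE |

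The texts agree in three rows and contradict each other in the fourth.

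**Step 2. Can the fourth row occur here?** The causal exception in Section 7.3.1.5 is worded for disease progression. Appendix 10 includes in progression a fall of at least 50% in granulocytes or platelets from best response, a haemoglobin fall of at least 2 g/dL, and transfusion dependence. Section 4.11.1 attributes falls in the same cell lines to the study drugs. A drug effect on counts can therefore meet the protocol's own definition of progression.

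**Step 3. Does Section 12.5.1 settle it alone?** No. A clinically significant platelet fall from baseline fits the inclusion. If it is also regarded as associated with MDS and no worse than expected, it fits the exclusion. No rule of precedence is given.

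**Step 4. What is exposed and what is not?**

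- Exposed: the AE and SAE components of the Part 1 primary endpoint and of the Part 2 safety endpoint.
- Not exposed: laboratory changes, which are graded by CTCAE from the data (Sections 9.4.2 and 9.4.2.3); DLTs and dose reductions or delays, which are separate components of the Part 1 endpoint; and deaths, which go on the Death eCRF (Section 7.3.1.5), into the death summaries (Section 9.4.2.2) and into overall survival.

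**Step 5. Scale.** With up to 6 subjects per dose level (Section 4.3.2), one unrecorded subject changes an incidence by 1/6 = 16.7 percentage points. With 28 subjects in a Part 2 arm (Section 4.8), the change is 1/28 = 3.6 points. These show what one subject weighs; they do not estimate how many would be lost.

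**The case against.** The best defence is that the exclusion is conditional. A cytopenia that the investigator attributes to the drug is, on a plain reading, not a disease-associated finding, and the inclusion list captures it. That stands for most drug-related cytopenia. It does not cover the fourth row, because progression is disease-associated by definition and Section 7.3.1.5 expressly allows it also to be treatment-caused.

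A second defence is that Section 7.3.1.5 exempts natural-course events by default and makes its causal exception only for progression, so it does not order the reporting of disease-related cytopenia, bleeding or infection in general. That also stands, and it limits the point to worsening that counts as progression, which Appendix 10 makes a matter of blood counts as well as blasts.

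A reader might infer more than the documents support:

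- *That Appendix 5 bars cytopenia from being an AE, or removes the drug's main toxicity from the Part 1 primary endpoint.* The severity exception, the inclusion list and the unaffected endpoint components rule this out.
- *That the seriousness examples contradict the exclusion.* "Examples of such events are invasive or malignant cancers, intensive treatment in an emergency room or at home for allergic bronchospasm, blood dyscrasias or convulsions" are generic examples under a clause that leaves reporting to judgement, and they apply only to events that are already AEs.
- *That listing hematologic events as being of special interest gives them another AE status.* Section 5.5.1.1 deals with their monitoring and management.
- *That an event can be a DLT yet not an AE because the causality standards differ.* A DLT counts "unless it can be clearly established that the event is unrelated to treatment", while Section 12.5.5 wants evidence for causality "rather than a relationship cannot be ruled out". Both concern relatedness, and AE status does not depend on relatedness.
- *That a loss rate or a difference between arms can be estimated.* The protocol gives no basis for either. In the sponsor's AML study, febrile neutropenia was an SAE in 6 subjects of 11 (Section 2.2.5), which shows such events being reported, not suppressed.

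**Conclusion.** The contradiction is real and confined to one case: disease worsening of expected severity that the investigator considers caused by study treatment or protocol procedures. Section 7.3.1.5 makes it a mandatory SAE report; Sections 12.5.1 and 12.5.2 say it cannot be one. Section 12.5.1 adds an unresolved overlap between its own inclusion and exclusion of clinically significant hematology findings. The case is reachable because progression in this protocol includes count-based criteria that the drugs' known toxicities can meet.

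The consequence is possible under-counting in the AE and SAE components of the two safety endpoints, not loss of the safety signal as a whole. Its size cannot be derived from the protocol. It depends on how often investigators judge a worsening to be both expected in severity and treatment-caused, and on which text they follow. The point is worth correcting because it concerns serious event reporting, the cohorts are small, and the correction is nearly free.

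**What to change.** Reconcile the passages in an amendment:

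1. Add the causal-relationship exception of Section 7.3.1.5 to both disease exclusions in Section 12.5.1 and to the first sentence of Section 12.5.2. A disease-associated finding or progression that the investigator considers caused by study treatment or protocol procedures is then an AE and, if serious, an SAE.
2. State that this exception prevails over the disease exclusions. This also settles the overlap within Section 12.5.1 for treatment-caused hematology worsening.
3. Cross-refer Section 7.3.1.5 to the seriousness criteria in Section 12.5.2, since its causal clause names none of its own.

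The cost is a few sentences and a few more AE and SAE reports. Recording every worsening in CTCAE count grade, and every bleed or infection, as an AE is not needed to remove the contradiction. It would be a debatable preference, and its count part would largely repeat the laboratory grading already planned.
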